7.1.3 Quality Assurance Audit

Study centers, the study database and study documentation may be subject to Quality Assurance audit during the course of the study by the Sponsor or the CRO on behalf of the Sponsor. In addition, inspections may be conducted by regulatory bodies at their discretion.

8.0 STATISTICS

The SAP will be finalized prior to randomization of the first 30% of the planned number of subjects. Further statistical details can be found by referring to the SAP. The basis for the analysis plan can be found in this section.

8.1 Determination of Sample Size

This study will have two primary efficacy endpoints (see Section 6.1.1).

For the primary efficacy endpoint OR at Study Day 28, it is assumed that the conventional treatment would have a response rate of 50%, and further assumed that the response rate for the BEGEDINA treatment arm would be 75%. In order to have 80% power for a one-sided test at $\alpha=0.025$, 58 patients per treatment group would be required.

For the other primary endpoint, TRM up to Study Day 180, the cumulative incidence for the conventional treatment is assumed to be 50% and the one for BEGEDINA is assumed to be 30% (relative reduction by 40%). 80% power for a one-sided log-rank test with significance level 0.025 requires a total of 103 deaths without prior diagnosis of relapse. These can be expected with 92 subjects per treatment group, provided there are no early dropouts and no diagnoses of relapse. If drop-outs or diagnoses of relapse are observed during the recruitment period, the sample size may be slightly increased, e.g., to 100 subjects per treatment group. Since the required sample size for TRM is larger than the one for overall response, a total sample size of 184 (up to 200, respectively) will be used.

Overall survival up to 180 days is the key secondary endpoint and the planned sample size provides adequate power to reject the null hypothesis of equal OS, assuming 20 to 25 percent differences in survival probabilities in favor of BEGEDINA.

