
Test product, dose and mode of administration:
	
BEGEDINA (murine monoclonal antibody against CD26, BT 5/9 antibody) 2.7 mg/m²/day for 5 consecutive days from Study Day 1 through to Study Day 5, and on Study Days 10, 14, 17, 21, 24, and 28.

Reference therapy, dose, and mode of administration:
	
Subjects in the conventional treatment arm will receive a single second-line treatment, according to the standard practice at the study center (physician's best choice).

Salvage treatment:
	
There are currently no recommended salvage (third-line) therapies for steroid-resistant acute GvHD; recommended treatment at this point could follow the European Group for Blood and Marrow Transplantation and the European LeukemiaNet or American Society of Blood and Marrow Transplantation (ASBMT) guidelines (per investigator discretion).

Sample size considerations: This study will have two primary efficacy endpoints as health authorities (EMA/FDA) have requested different primary endpoints: OR at Study Day 28 is the single primary endpoint for FDA, TRM up to Day 180 is the single primary endpoint for EMA.
 
For OR at Study Day 28, it is assumed that the OR rate for conventional treatment would be 50% and that the OR rate for BEGEDINA would be 75%. In order to have 80% power for a one-sided test at $\alpha=0.025$, 58 patients per treatment are required.
 
For the other primary endpoint, TRM up to Study Day 180, the cumulative incidence for the conventional treatment is assumed to be 50% and the one for BEGEDINA is assumed to be 30% (relative reduction by 40%). 80% power for a one-sided log-rank test with significance level 0.025 requires a total of 103 transplant-related deaths. These can be expected with 92 subjects per treatment group, provided there are no early dropouts and no diagnoses of relapse. If drop-outs or diagnoses of relapse are observed during the recruitment period, the sample size may be slightly increased, e.g., to 100 subjects per treatment group.
 
Since the required sample size for TRM is larger than the one for OR, a total sample size of 184 (up to 200, respectively) will be used. The planned sample size will also provide adequate power to reject the null hypothesis of equal OS up to Study Day 180 (key secondary efficacy endpoint) assuming 20 to 25 percent differences in survival probabilities in favor of BEGEDINA.
	

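### The TRM sample size asks for 103 deaths and expects them from 92 per group, but the plan's own 50% and 30% incidences give about 74

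*Combined protocol and SAP*

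**What the plan says.** Section 8.1 sizes the trial on TRM, because TRM needs more subjects than overall response. It states that "the cumulative incidence for the conventional treatment is assumed to be 50% and the one for BEGEDINA is assumed to be 30" per cent, described as a 40% relative reduction. The test is specified as "80% power for a one-sided log-rank test with significance level 0.025". The section then says that this "requires a total of 103 deaths without prior diagnosis of relapse. These can be expected with 92 subjects per treatment group", on condition that there are no early drop-outs and no relapse diagnoses. If either occurs during recruitment, the number may rise to about 100 per group.

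The synopsis (Sample size considerations) carries the same numbers: "requires a total of 103 transplant-related deaths. These can be expected with 92 subjects per treatment group".

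Section 6.1.1.2 defines the event as death without a prior relapse diagnosis and censors survivors at Study Day 180. Section 8.3.5.1 places TRM first in the EMA testing sequence.

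**The concern.** A number of subjects multiplied by an assumed incidence gives the expected number of events. Here 92 per group at 50% and 30% cannot give 103. Reaching 103 deaths among 184 subjects would need a pooled incidence of 103/184 = 56%, which is higher than the rate assumed for either arm. Longer follow-up cannot supply the missing deaths, because TRM is censored at Day 180, the same horizon as the incidences.

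This paragraph justifies the size of the whole trial and of the single EMA primary endpoint. A reader cannot tell which assumption is in force. Judged against 103, a trial running exactly to plan would look about 29 deaths short, and the increase to 200 subjects could not close the gap.

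**Working it through.** **Inputs.** Day 180 TRM incidence 50% (conventional) and 30% (BEGEDINA), one-sided alpha 0.025, 80% power, log-rank test, 92 per group or up to 100, no drop-out or relapse (section 8.1). Allocation is 1:1 (section 4.1). Follow-up is fixed at 180 days (section 6.1.1.2).

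**Expected deaths**
- 92 per group: 92 x 0.50 + 92 x 0.30 = 46 + 27.6 = 73.6. Shortfall: (103 - 73.6)/103 = 29%.
- 100 per group: 50 + 30 = 80.
- Subjects needed to see 103 deaths: 103/0.40 = 257.5, so 258. This is the number that would reach the stated count, not the number needed for 80% power.

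**Required deaths.** With proportional hazards, HR = ln(0.70)/ln(0.50) = 0.5146 and ln(HR) = -0.6644. Also (1.960 + 0.8416)^2 = 7.849.
- Schoenfeld: 4 x 7.849 / 0.6644^2 = 71.1, so 72.
- Freedman: 7.849 x (1.5146/0.4854)^2 = 76.4, so 77.

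**Trying to reproduce 103.** None of the readings of the stated inputs that were tried gives it as an event count at 80% power.
- Reading the 40% reduction as HR 0.60: 121 (Schoenfeld) or 126 (Freedman).
- Entering 50% and 30% as survival: HR = ln(0.50)/ln(0.30) = 0.5757, Schoenfeld 102.98, so 103. But 92 per group would then give 92 x (0.50 + 0.70) = 110.4 deaths.
- Freedman at HR 0.515 with 90% power: 102.3, so 103. The plan says 80%.
- Two-proportion formula with continuity correction: 103, but as subjects per group.

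The response calculation in the same section (50% versus 75%, 58 per group) does reproduce, using the pooled two-proportion formula.

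**Power at the expected count.** Schoenfeld: z = sqrt(D) x 0.6644/2 - 1.960. Freedman: z = sqrt(D) x 0.4854/1.5146 - 1.960.
- D = 73.6: z = 0.890, power 81% (Schoenfeld); z = 0.790, power 79% (Freedman). A simulated log-rank test gives 80.7%.
- D = 80: 84% and 82%.
- D = 103: 92% and 90%.

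**Effect of relapse.** The plan gives no relapse rate for sizing, so these rates are assumptions: equal in both arms, constant cause-specific hazards, with r the 180-day relapse risk in the absence of death. With a = -ln(S), S = 0.50 or 0.70, and b = -ln(1 - r), the TRM incidence in an arm is a/(a + b) x [1 - S(1 - r)]. At r = 20% this gives 0.454 and 0.271, so 92 x 0.725 = 67 deaths.

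| Assumed r | Per group | Expected deaths | Power (Freedman to Schoenfeld) |
|---|---|---|---|
| 0% | 92 | 74 | 79-81% |
| 12.5% | 92 | 69 | 76-79% |
| 20% | 92 | 67 | 74-77% |
| 20% | 100 | 72 | 78-81% |
| 30% | 92 | 63 | 72-75% |

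Simulations that either censored relapse or kept relapsed subjects in the risk set agreed to within about two percentage points.

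**The case against.** The strongest reply is that the error does no harm. The planned number is adequate on the plan's own assumptions: 92 per group gives about 80% power for 50% versus 30%. The trial is not event-driven. The interim in section 8.6 is timed by Day 28 response data, and the increase to 200 is triggered by observed drop-outs or relapses, not by a death count. No rule in the document uses 103.

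Most of this stands. The finding must not be read as saying that 184 subjects are too few for 50% versus 30%, and harm to a decision is conditional on someone using 103. But the number is the stated requirement for the EMA primary endpoint, and the decision to go from 184 to 200 has no other TRM benchmark. If the conditional power in section 8.6 were projected for TRM, 103 would overstate the final information by 103/73.6, or about 40%.

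The origin of 103 is also open. Entering the incidences as survival fits to the decimal, but it is not the only route to 103 and it does not explain 92 per group. The document leans towards the incidences being right and the event count wrong: the 40% relative reduction matches 50% to 30%, whereas 70% to 50% is 20/70 = 29%. Section 2.3 also cites 28.6% Day 180 TRM for the chosen schedule, which is close to 30%.

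**Conclusion.** The concern holds. The death count of 103, the incidences of 50% and 30%, and 92 per group cannot all be true. On the stated incidences, 74 deaths are expected and 72 to 77 are needed for 80% power. The stated count is therefore wrong both as a requirement and as an expectation.

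The expected count rests only on the plan's incidences and its condition of no drop-out or relapse. The required count also assumes proportional hazards. Power at 92 per group is about 80% with no margin, and it falls to roughly 74-77% at an assumed 20% relapse risk. That the incidences were entered as survival probabilities is a plausible cause, not an established one. The correction must be made, because the written justification for the EMA primary endpoint is arithmetically impossible.

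**What to change.** Correct section 8.1 and the synopsis together.

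- Delete 103. State HR 0.515 and 72 required deaths (Schoenfeld; 77 by Freedman) for 80% power at one-sided 0.025, and name the formula used.
- State that 92 per group is expected to give about 74 deaths (power about 80%) and 100 per group about 80 deaths (82-84%), both without relapse or drop-out.
- Tie the decision to go from 184 to 200 subjects to the corrected count, and show expected deaths and power at assumed relapse rates of 10-20%.
- If 30% versus 50% survival was the real assumption, restate the incidences as 70% and 50%, the expected deaths at 92 per group as about 110, and remove the 40% relative reduction.
- Check that no other trial document, including the DSMB analysis plan, uses 103 as a target or an information denominator.

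The cost is a text change in two places and no additional patients. The power statement becomes slightly less favourable once relapse is allowed for.

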8.2 Analysis Sets

Full Analysis Set

The FAS comprises all subjects to whom study treatment has been randomized. Statistical analyses will be based on study treatment groups as per randomization (and strata used within randomization), irrespective of the study treatment actually received. The FAS will be used for demographics, baseline disease characteristics and all efficacy analyses.

Safety Analysis Set

The Safety Analysis Set (SAF) includes all subjects who received at least one dose of study treatment. Subjects will be analyzed according to the study treatment (regimen) they actually received: if a subject has received any dose of BEGEDINA, the subject is assigned to the

Confidential

BEGEDINA group within the Safety Analysis Set; otherwise the subject is assigned to the conventional treatment group. The Safety Analysis Set will be used for all safety analyses.

Pharmacokinetic analysis set

The pharmacokinetic analysis set consists of all subjects randomized to BEGEDINA with at least one study drug concentration value.

8.3 Statistical Methods

Descriptive statistics [e.g., number of subjects, mean and standard deviation, median, minimum, and maximum] will be provided for continuous variables and frequency counts and percentages will be displayed for categorical variables. All outputs will be generated by study treatment group.

All statistical tests will be conducted at a one-sided significance level of 2.5% unless otherwise specified. Treatment effect estimates will be reported with two-sided 95% confidence interval (CI).

8.3.1 Analysis of Demographics and Baseline Disease Characteristics

Demographics and baseline disease characteristics will be summarized by descriptive statistics.

Demographic data will include: gender, age, race and ethnicity, smoking status (never smoked, current smoker, previous smoker), weight, height, BMI. Baseline disease characteristics will include: medical history and medications related to GvHD, general medical history, physical examinations, vital signs, donor compatibility, HSCT source, grade of acute GvHD at onset, and grade of acute GvHD at baseline.

8.3.2 Analysis for Extent of Exposure

Extent of exposure to study treatment will be summarized by visit as well as for duration of study medication (date of last dose minus date of first dose +1).

8.3.3 Analysis of Concomitant Medication for Treatment of aGvHD

Treatments of acute GvHD will be tabulated, separately prior to randomization and after randomization.

8.3.4 Analysis of Primary Efficacy Endpoints

There are two primary efficacy endpoints as health authorities (EMA/FDA) have requested different primary endpoints: OR at Study Day 28 (see Section 6.1.1.1) is the single primary

endpoint for FDA, TRM up to Day 180 (see [Section 6.1.1.2](#)) is the single primary endpoint for EMA. The analysis methods are:

- the null hypothesis of equal OR probabilities for BEGEDINA and conventional treatment will be tested using a Cochran-Mantel-Haenszel test stratified for baseline GvHD severity grade (as used in the randomization) at the one-sided $\alpha = 0.025$ level. The treatment effect will be expressed as odds ratio with a two-sided 95% CI.
- TRM up to Study Day 180 will be graphically displayed by non-parametric cumulative incidence curve estimates. The null hypothesis of same TRM (defined as death without prior diagnosis of relapse) cumulative incidences for both study treatments will be tested by a one-sided test stratified for the baseline GvHD severity grade (as used in the randomization) taken into account the competing risk of relapse diagnosis. The one-sided significance level is set to $\alpha = 0.025$. Regression analysis of cause-specific hazards stratified for the baseline GvHD severity will be performed as supportive analysis in order to quantify the treatment effect in terms of hazard ratios and two-sided 95% CI.

8.3.5 Analyses of Secondary Efficacy Endpoints

8.3.5.1 Analysis of Key Secondary Efficacy Endpoint

The null hypothesis of same OS curves (up to Study Day 180) for both study treatments will be tested by a one-sided log-rank test stratified for the baseline GvHD severity grade (as used in the randomization). The one-sided significance level is set to $\alpha = 0.025$. A proportional hazards regression analysis stratified for the baseline GvHD severity will be performed as supportive analysis in order to quantify the treatment effect in terms of a hazard ratio and a two-sided 95% CI. OS will be graphically displayed by Kaplan-Meier plots.

The following two sequential testing procedures will be applied to control the one-sided type-I-error probability by 0.025:

A. For the primary endpoint preferred by the FDA:

1. Test of “OR at Day 28” by a stratified Cochran-Mantel-Haenszel test with one-sided significance level 0.025
2. Only if significant, then test “OS up to Study Day 180” by a stratified log-rank test with one-sided significance level 0.025
3. Only if significant, then test “TRM up to Study Day 180” by a stratified log-rank test with one-sided significance level 0.025.

Whenever a test does not lead to rejection of a null hypothesis, the test procedure A will be stopped.

B. For the primary endpoint preferred by the EMA:

1. “TRM up to Study Day 180” by a stratified log-rank test with one-sided significance level 0.025.
2. Only if significant, then test “OR at Study Day 28” by a stratified Cochran-Mantel-Haenszel test with one-sided significance level 0.025.
3. Only if significant, then test “OS up to Study Day 180” by a stratified log-rank test with one-sided significance level 0.025

Whenever a test does not lead to rejection of a null hypothesis, the test procedure B will be stopped.

8.3.5.2 Analysis of Other Secondary Efficacy Endpoints

All other secondary and supportive analyses will be tested at a one-sided $\alpha=0.025$ significance level (where applicable), with no adjustments for multiplicity. These endpoints and their statistical analysis method are:

- Change from baseline in stages of GvHD by target organ at Study Day 28: shift tables displaying the frequencies for each possible change from baseline to Study Day 28.
- Cumulative incidence of chronic GvHD up to Study Day 180 will be graphically displayed by non-parametric cumulative incidence curve estimates. The null hypothesis of same cumulative incidences (up to Study Day 180) for both study treatments will be tested by a one-sided test stratified for the baseline GvHD severity grade, taken into account the competing risk of death. Stratified regression analysis of cause-specific hazards will be performed as supportive analysis in order to quantify the treatment effect in terms of hazard ratios and two-sided 95% CI. The cumulative steroid dose on Study Days 28, 56 and 90: descriptive statistics and non-parametric Wilcoxon-Mann-Whitney test stratified by for the baseline GvHD severity grade.
- Cumulative incidence of relapse up to Study Day 180 will be graphically displayed by non-parametric cumulative incidence curve estimates. The null hypothesis of same cumulative incidences (up to Study Day 180) for both study treatments will be tested by a one-sided test stratified for the baseline GvHD severity grade, taken into account the competing risk of death prior to diagnosis of relapse. Stratified regression analysis of cause-specific hazards will be performed as supportive analysis in order to quantify the treatment effect in terms of hazard ratios and two-sided 95% CI.
- Cumulative incidence of relapse-related mortality up to Study Day 180 will be graphically displayed by non-parametric cumulative incidence curve estimates. The null hypothesis of

same cumulative incidences (up to Study Day 180) for both study treatments will be tested by a one-sided test stratified for the baseline GvHD severity grade, taken into account the competing risk of transplant-related death (defined in Section 6.1.1.2). Stratified regression analysis of cause-specific hazards will be performed as supportive analysis in order to quantify the treatment effect in terms of hazard ratios and two-sided 95% CI.

- Change from baseline in Karnofsky Performance Status scale: shift tables displaying the frequencies for each possible change from baseline.

8.3.6 Analyses of Exploratory Efficacy Endpoints

Any further exploratory efficacy endpoints will be summarized by descriptive statistics. These endpoints include:

- The change in QoL from baseline based on the SF36.
- Duration of response.
- Overall response by standard-risk and high-risk GvHD ([MacMillan et al., 2015](#)).

8.3.7 Safety Analyses

For each study treatment, numbers of AEs and incidence rates will be tabulated by MedDRA system organ class and preferred term. An event that occurred one or more times on the date of, or subsequent to, randomization will contribute one observation to the numerator of the incidence rate. The denominator of the rate will comprise all randomized subjects exposed to the study treatment. If the intensity or seriousness of the AE changes, then the overall intensity or seriousness will be the maximum intensity or seriousness of the multiple occurrences.

Serious adverse events, AEs leading to death and AEs leading to withdrawal of subjects will be tabulated for each treatment group. Commonly occurring AEs, i.e. those which occur in 5% or more of the subjects in either treatment group, will be summarized using descriptive statistics.

Descriptive statistics will be used to present physical examination results, weight, BMI, vital signs measurements; clinical laboratory test results; and ECG results – for both raw values and change from baseline. Shift tables will be presented for selected tests.

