Exposure

Thirteen patients received 5 planned consecutive daily doses of BEGEDINA 2 mg/kg.

Three subjects received a second cycle of five days treatment and one patient received three additional days of treatment.

Summary of adverse events

An overview of the adverse events (AEs) reported during the study is presented in Table 4.

All 13 subjects (100.0%) reported at least one AE. Death occurred by Day +365 in 8 subjects (61.5%) and SAEs were reported in 9 subjects (69.2%). All 13 subjects (100.0%) had at least one Grade ≥ 3 AE. Treatment-related AEs were reported in 5 subjects (38.5%). No subject discontinued the study due to AEs.

Table 4 Summary of Adverse Events (Pilot Study, EudraCT No. 2007-005809-21)

	Safety Population (N=13)
Number of deaths, N (%) , E	8 (61.5%), 12
AEs, N (%) , E	13 (100.0%), 488
SAEs, N (%) , E	9 (69.2%), 27
Grade \geq 3 AEs, N (%) , E	13 (100.0%), 70
Treatment-related AEs, N (%) , E	5 (38.5%), 8
AEs leading to treatment discontinuation, N (%) , E	0 (0.0%), 0

Abbreviations: AE, adverse events; E, number of events; N, number of subjects; SAE, serious adverse event.

Source: Clinical study report, EudraCT No. 2007-005809-21, Section 14, Table 14.3.1.1

The safety profile of BEGEDINA was good and no allergic AEs were reported for any subject.

The most commonly presented AEs by preferred term (in at least 25% of subjects overall) are presented in Table 5.

Table 5 Most Commonly Reported Adverse Events (in at least 25% Subjects), All Causality (Safety Population)

System Organ Class Preferred Term	Safety Population (N=13) N (%), E
Blood and Lymphatic System Disorders	10 (76.9%) 24
Leukopenia	4 (30.8%) 8
Pancytopenia	4 (30.8%) 5
Gastrointestinal Disorders	12 (92.3%) 73
Abdominal pain	6 (46.2%) 13
Diarrhoea	11 (84.6%) 24
Nausea	4 (30.8%) 11
Vomiting	5 (38.5%) 9
General Disorders and Administration Site Conditions	11 (84.6%) 20
Asthenia	4 (30.8%) 5
Pyrexia	6 (46.2%) 9
Immune System Disease	10 (76.9%) 80
GvHD in intestine	8 (61.5%) 25
GvHD in liver	7 (53.8%) 22
GvHD in skin	7 (53.8%) 31
Infections and Infestations	12 (92.3%) 55
Cytomegalovirus infection	8 (61.5%) 24
Investigations	13 (100.0%) 57
Blood bilirubin increased	4 (30.8%) 8
Gamma-glutamyl transferase increased	5 (38.5%) 12
Metabolism and Nutrition Disorders	8 (61.5%) 14
Decreased appetite	4 (30.8%) 5
Musculoskeletal and Connective Tissue Disorders	8 (61.5%) 23
Sjorgen's syndrome	4 (30.8%)

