4.4.4.1 Reason for Withdrawal/Discontinuation

All subjects are free to withdraw from participation in the study at any time, for any reason, specified or unspecified, and without prejudice to further treatment. The criteria for enrollment are to be followed explicitly.

If a subject who does not meet enrollment criteria is inadvertently enrolled, the Sponsor or Sponsor designee (Contract Research Organization [CRO]) must be contacted to evaluate if the subject is to continue treatment. In these rare cases, the investigator must obtain documented approval to allow the subject to continue study treatment.

In addition, subjects will be discontinued from study drug (but not withdrawn from the study and subsequent assessments) in the following circumstances:

- The investigator decides that the subject's treatment should be discontinued. If this decision is made because of an intolerable AE or a clinically significant laboratory value, which compromises the safety, health or welfare of the subject, the study drug is to be discontinued and appropriate measures are to be taken. The Sponsor or Sponsor designee is to be notified immediately.
- Lack of compliance with protocol.

If a subject discontinues from study drug but continues in the study for follow up, a last PK sample should be collected on the next scheduled visit after study drug discontinuation. No further samples will be required. HAMA and other scheduled assessments are to be followed as per protocol.

Subjects will be discontinued from study drug and withdrawn from the study protocol in the following circumstances:

- The subject is unwilling to continue in the study and consent is withdrawn by the subject or their legal guardian. A subject may choose to discontinue treatment but agree to be followed for study endpoints and safety, as per 4.4.4.2 below.
- Lost to follow-up.
- Death.

Subjects who are withdrawn from the study early will have early termination procedures performed as shown in the Schedule of Events (Table 19). Subjects who are withdrawn from the study will not be replaced (see Section 4.4.4.3).

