5.11 Dose Modification for Toxicity

No specific toxicities have been observed to date with BEGEDINA.

Important identified risks include the development of HAMA and infusion-related reactions (described in Section 5.1.1).

Therefore, dose modification for toxicity is left to the discretion of the Principal Investigator. However, treatment should be delayed/withdrawn in case of severe (Grade 3 or above) toxicity considered related to the study treatment or that, in the opinion of the investigator, might be life-threatening if treatment is continued.

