- Not related: The event or laboratory test abnormality is most likely produced by other factors such as the subject's clinical condition, intercurrent illness, or concomitant drugs, and does not follow a known response pattern to the study drug, or the temporal relationship of the event to study drug administration makes a causal relationship unlikely.
- Possibly related: The event or laboratory test abnormality follows a reasonable temporal sequence from the time of drug administration, and/or follows a known response pattern to the study drug, but could have been produced by other factors such as the subject's clinical condition, intercurrent illness, or concomitant drugs. Information on drug withdrawal may be lacking or unclear.
- Probably related: The event or laboratory test abnormality follows a reasonable temporal sequence from the time of drug administration, and/or follows a known response pattern to the study drug, and unlikely to be explained by other factors such as the subject's clinical condition, intercurrent illness, or concomitant drugs. There is a positive response to drug withdrawal. Rechallenge is not required.
- Certainly related: The event or laboratory test abnormality follows a reasonable temporal sequence from the time of drug administration, and/or follows a known response pattern to the study drug, and cannot be reasonably explained by other factors such as the subject's clinical condition, intercurrent illness, or concomitant drugs. There is a positive response to drug withdrawal. Rechallenge is positive.

Adverse Events with a causality of “Possibly”, “Probably” or “Certainly” related meet criteria of ADRs.

All efforts should be made to classify the AE according to the above categories.

Action Taken

Action taken with study treatment due to the event which bases on the following categories:

- None (when no action is undertaken with the investigational product due to the event)
- Drug temporarily withdrawn

- Drug permanently withdrawn

Outcome of AE

Adverse events may result in one of the following outcomes:

- Death (only if the AE term reported is considered to be the cause of Death. Please note: for consistency, if outcome is ‘Death’ also seriousness must be ‘Death’)
- Recovered/resolved
- Recovered with sequelae
- Recovering/resolving
- Not Recovered/resolved: the event does not resolve

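### The planned table of AEs leading to withdrawal of subjects omits AE-driven stops of study drug in subjects who stay in follow-up, and no other planned output covers them

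*Combined protocol and SAP*

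**What the plan says.** Section 8.3.7 plans tables of AEs by system organ class and preferred term, a summary of common AEs, and three special categories: "Serious adverse events, AEs leading to death and AEs leading to withdrawal of subjects will be tabulated for each treatment group".

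Section 4.4.4.1 defines two ways of stopping.

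- **Study drug only.** The text reads "subjects will be discontinued from study drug (but not withdrawn from the study and subsequent assessments) in the following circumstances". The first circumstance listed is the investigator's decision to stop treatment, and the AE case sits there: "If this decision is made because of an intolerable AE or a clinically significant laboratory value". The other is non-compliance.
- **Study drug and study.** The text reads "Subjects will be discontinued from study drug and withdrawn from the study protocol in the following circumstances". The list is withdrawn consent, loss to follow-up and death. An AE is not listed as a reason in its own right.

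Section 4.4.4.2 repeats the distinction. A subject who stops treatment for any reason is asked to stay for endpoint follow-up and counts as withdrawn from treatment, not from the study.

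Under Action Taken, section 6.2.1.1 has the investigator record for each AE one of three actions: none, temporary withdrawal of drug, or "Drug permanently withdrawn".

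**The concern.** Section 3.1.3 makes comparison of safety and tolerability between the arms a secondary objective. How often an AE led to study drug being stopped is a direct measure of tolerability, and the protocol expects such stops. Section 5.11 calls for delay or withdrawal of treatment for certain severe toxicities, and section 5.1.1.1 foresees that some subjects may be barred from further infusions.

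The planned category is defined by the subject leaving the study, whereas the protocol directs a subject with an intolerable AE to stop drug and stay in. The table could therefore miss the events that a reader would look for in it.

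There is a link to the reading of a primary endpoint. Section 5.7.2 allows third-line treatment for subjects who cannot tolerate randomized treatment, and section 6.1.1.1 counts third-line therapy before the Day 28 assessment as non-response. Without a table of AE-driven stops, it is harder to tell how much of the non-response in each arm came from intolerance and how much from lack of effect.

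**Working it through.** The plan gives no figure on this point and none is needed. The check sets the passages side by side.

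1. **What the table counts.** Section 8.3.7: "AEs leading to withdrawal of subjects will be tabulated for each treatment group". The object of the withdrawal is the subject, not the drug.
2. **Where an AE-driven stop falls.** Section 4.4.4.1 places it under discontinuation of drug, with the subject expressly kept in the study. Section 4.4.4.2 agrees.
3. **What can still enter the table.** Section 4.4.4.1 lets a subject leave at any time for any reason, and withdrawn consent is a listed route out of the study. An AE may prompt that. Death is also a listed route. The category therefore has content, but only AEs that ended participation.
4. **What is left out.** A subject whose drug is stopped for an AE and who continues to be assessed meets the definition in step 2 and not that in step 1.
5. **Whether another output covers it.** Section 8.3.2 summarises exposure by visit and duration from first to last dose, without reasons for stopping. The remaining parts of section 8.3 name no summary of reasons for stopping drug and no output based on the action-taken field. The general AE tables in 8.3.7 include the AE itself but do not show that it led to a stop.
6. **Whether the data exist.** They do. The action-taken item in 6.2.1.1 separates permanent from temporary withdrawal for each AE.
7. **What the earlier studies reported.** The AE summaries of the pilot study (Table 4) and the dose-finding study (Table 12) each have a row for "AEs leading to treatment discontinuation". The category in 8.3.7, read literally, is not the same one.

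A related comparison concerns dose changes. Section 5.11 says that "dose modification for toxicity is left to the discretion of the Principal Investigator". Section 5.13 says that the prescribed dosage, timing and mode of administration are not to be altered, and that departures go in the eCRF. The codes in 6.2.1.1 include no dose change. These three places do not agree.

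**The case against.** The strongest reply is that the protocol does not use the word withdrawal strictly. Section 4.4.4.2, on handling withdrawals, also covers treatment stops. Section 5.11 speaks of treatment being withdrawn, and the code in 6.2.1.1 is "Drug permanently withdrawn". That code is the natural source for a table of AEs leading to withdrawal, so the sponsor may have meant drug stops all along. The accounts of the earlier studies point the same way: their text says that no subject left the study because of AEs, while the tables label the same zero as treatment discontinuation. Section 8.0 also defers further detail to the SAP, and no SAP text beyond section 8 is in the document reviewed. The synopsis plans AE listings for each subject, so nothing is lost from the data.

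Much of this stands. Omission is the result of reading 8.3.7 with the protocol's own definitions; it is not a certainty about what will be programmed. But loose usage elsewhere does not settle the sentence, because two programmers could build different tables from it. Section 8.0 calls section 8 the basis for the SAP, so the category should be right there.

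Three stronger readings are tempting, and the documents do not support them.

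- A reader might infer that an AE can never withdraw a subject, so that the table would be empty apart from deaths, or near zero in both arms. It would not necessarily be: consent may be withdrawn because of an AE.
- A reader might try to size the gap from the earlier studies, where none of 13 + 16 = 29 treated subjects had an AE leading to treatment discontinuation. Those subjects had different regimens, and only the 7 in the DL2bis cohort were on the 11-dose schedule (5 + 6 doses). The pooled count does not describe this trial.
- A reader might infer that 6.2.1.1 simply lacks a dose-change code that should be added. Section 5.13 says that the dosage may not be changed and already requires departures to be recorded, so the inconsistency has to be resolved first.

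**Conclusion.** The point holds in limited form. Under the definitions in 4.4.4.1 and 4.4.4.2, the withdrawal category in 8.3.7 captures AEs that end study participation and omits AE-driven treatment stops in subjects who remain in follow-up. No other planned output reports those stops. The stated category is the wrong one for the tolerability objective, so this is more than missing detail.

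The omission covers both permanent and temporary stops, in either arm. Its numerical size cannot be derived from the documents. No primary or key secondary test, significance level or sample size is affected.

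The conclusion assumes that 8.3.7 uses withdrawal of subjects in the sense of 4.4.4.1, and that the SAP does not add the missing table. If the SAP does add it, what remains is a wording correction to 8.3.7.

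**What to change.** In section 8.3.7, and in the SAP to match, tabulate by treatment arm the AEs whose action taken is permanent withdrawal of drug and, separately, those whose action taken is temporary withdrawal. Use the field already collected under 6.2.1.1. Keep AEs leading to withdrawal from the study as a distinct third category, labelled with the wording of 4.4.4.1.

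The cost is one sentence in 8.3.7 and one table. No new data are needed for it.

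Separately, the sponsor should reconcile section 5.11, section 5.13 and the action-taken codes in 6.2.1.1 on whether a dose may be changed for toxicity and how such a change is recorded. No dose rule or code is proposed here.
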